## 10.5. Statistical Methods

For continuous variables, descriptive statistics will include the following: the number of patients reflected in the calculation (n), mean, standard deviation, median, first quartile (Q1), third quartile (Q3), minimum, and maximum.

For categorical or ordinal data, frequencies and percentages will be displayed for each category.

All data will be summarized by 3 treatment groups (ie, dupilumab Q2W dose, dupilumab Q4W dose, and placebo). All placebo patients will be pooled for analysis regardless of whether it is 100 mg placebo, 200 mg placebo, or 300 mg placebo.

### 10.5.1. Demography and Baseline Characteristics

Demographic and baseline characteristics will be summarized descriptively by treatment group.

### 10.5.2. Efficacy Analyses

For each dose regimen and all efficacy variables, the analysis will be comparisons of each of the dupilumab treatment groups with the placebo group (Q2W and Q4W combined).

A sensitivity analysis for the primary endpoint and selected secondary endpoints will be performed in the mFAS.

#### 10.5.2.1. Primary Efficacy Analysis

The Cochran-Mantel-Haenszel test adjusted by randomization strata (baseline weight group and region) will be used for analyzing the percentage of patients with IGA 0 or 1 at week 16 or percentage of patients with EASI-75 at week 16. The Mantel-Fleiss (MF) criterion will be checked, and if it is not met, sensitivity analyses including each stratification factor separately in CMH test will be conducted.

All efficacy data regardless if the patient is on the study treatment or discontinues the study treatment but remains in the study will be used for analysis. Specifically, if a patient stays in the study until the end of the planned placebo-controlled treatment period, all efficacy data collected up to the planned end of treatment visit will be included in the primary analysis regardless if the patient is on treatment or not.

To account for the impact of rescue treatment on the efficacy effect: For the primary efficacy endpoints (which are binary efficacy endpoints), if rescue treatment is used (see Section 7.3), the patient will be specified as a nonresponder from the time the rescue is used.

If a patient withdraws from study, this patient will be counted as a nonresponder for endpoints after withdrawal.

Sensitivity analysis using the last observation carried forward (LOCF) approach to determine patient's status at week 16 will be conducted to assess the robustness of the primary efficacy analysis with regards to handling of missing data. The efficacy data will be set to missing after rescue treatment is used, then the LOCF method will be used to determine patients' status at week 16.

In addition, the Cochran-Mantel-Haenszel method adjusted by randomization strata will also be performed on all observed data regardless if rescue treatment is used. A patient with missing data will be counted as a non-responder. Other sensitivity analyses may be conducted.

### 10.5.2.2. Secondary Efficacy Analysis

For binary endpoints, the secondary efficacy analysis will use the same approach as that used for the primary analysis.

For continuous endpoints:

- The multiple imputation (MI) with analysis of covariance (ANCOVA) model will be used as the primary analysis method. Patients' efficacy data through week 16 after the rescue treatment use will be set to missing first, and then be imputed by the multiple imputation method. Missing data from the FAS will be imputed 40 times to generate 40 complete datasets by using the SAS procedure MI following the 2 steps below:
  - Step 1: The monotone missing pattern is induced by Markov Chain Monte Carlo (MCMC) method in MI procedure using seed number 12345.
  - Step 2: The missing data at subsequent visits will be imputed using the regression method for the monotone pattern with seed number 54321 and adjustment for covariates including treatment groups, randomization strata (baseline weight group and region), and relevant baseline.
- The week 16 data of each of the 40 complete datasets will be analyzed using an analysis of covariance (ANCOVA) model with treatment, randomization strata (baseline weight group and region), and relevant baseline included in the model, and the SAS MIANALYZE procedure will be used to generate valid statistical inferences by combining results from the 40 analyses using Rubin's formula.
- If a patient receives rescue treatment, the efficacy data collected after rescue treatment is initiated will be treated as missing. All efficacy data will be used for analysis regardless of whether the patient is on study treatment or discontinues the study treatment but remains in the study.
- In addition to the MI method described above, sensitivity analyses such as ANCOVA model with LOCF, MI method with ANCOVA model on all observed data regardless of rescue use will be conducted. Additional details on sensitivity analyses will be provided in the SAP.

Time to event endpoint will be analyzed using the Cox proportional hazards model. Kaplan-Meier curves will also be provided.

### 10.5.2.3. Multiplicity Considerations

A hierarchical procedure will be used to control the overall Type-1 error rate at 0.05 for the primary endpoint and the secondary endpoints across the 2 dupilumab dose regimens vs placebo. The abbreviated, preliminary plan for hierarchical testing order for the primary endpoint and key secondary endpoints is shown in [Table 3](#). The complete hierarchy including all the secondary endpoints will be provided in the SAP.

**Table 3: Preliminary Statistical Hierarchy for Multiplicity Control**

Endpoints		Dupilumab	
		q4w group	q2w group
Primary endpoint	Proportion of patients with IGA 0 to 1 (on a 5-point scale) at week 16	5	1
Co-primary endpoint for EMA and EMA Reference Market Countries only, key secondary for US	Proportion of patients with EASI-75 ( $\geq 75\%$ improvement from baseline) at week 16	6	2
Key Secondary endpoints	Percent change in EASI score from baseline to week 16	7	3
	Percent change from baseline to week 16 in weekly average of daily worst itch score	8	4

#### 10.5.2.4. First-Step Analysis

A first-step analysis may be performed when the last patient completes 16 weeks of treatment duration, in order to expedite the submission to regulatory agencies. No changes in the conduct of the study will be made based on this first-step analysis. The assessment of primary and secondary endpoints specified in Section 4.2.1 and Section 4.2.2 performed during the analysis will be the final analysis of the primary endpoint and secondary endpoints. Hence there will be no need for alpha adjustment due to the first-step analysis.

If a decision is made to perform the first-step analysis, in order to maintain study integrity with respect to the post-treatment follow-up visits, safety visits and analyses, a dissemination plan will be written. This plan will clearly identify the team (including the statistician) that will perform the first-step analysis and all related activities, restrict other clinical team members and other Sponsor personnel from access to individual patient treatment allocation and site level analysis results, and ensure that the dedicated team will not participate in the data review or data decisions for the following post treatment analyses. However, the dedicated team can participate in the analysis following the final database lock.

#### 10.5.3. Safety Analysis

Safety analysis will be based on the SAF. This includes reported TEAEs, AESIs, and other safety information (eg, clinical laboratory evaluations, vital signs, and 12-lead ECG results). A summary of safety results for each treatment group will be presented. In addition, safety data for the placebo Q2W group and placebo Q4W group will be summarized separately.

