For the 200 mg Q2W regimen in children aged  $\geq 6$  to  $< 12$  years old who weigh  $> 30$  kg, the simulated exposure substantially overlaps with the efficacious exposure in adults from studies R668-AD-1021, R668-AD-1334, R668-AD-1416 and R668-AD-1224 (300 mg Q2W and QW). In addition, in study DRI12544 (a phase 2b study in patients with moderate to severe uncontrolled asthma) (300 mg Q2W) a strongly positive benefit-risk was identified. Hence, the proposed 200 mg Q2W dosing regimen for children aged  $\geq 6$  to  $< 12$  years old weighing  $> 30$  kg is expected to have a significant clinical benefit with an appropriate safety profile, under the assumption that PK/PD relationship is similar in pediatrics and adult patients.

A dose regimen of 100 mg Q2W SC has not been evaluated to date in the dupilumab program. However, based on simulations from the PK model, the use of 100 mg Q2W is expected to provide mean exposure in children  $\geq 6$  to  $< 12$  years old who weigh  $< 30$  kg that is similar to that for 200 mg Q2W in children  $> 30$  kg, thereby supporting the use of this regimen in the lower weight group. Moreover, the 100 mg dose can be delivered using a lower volume of injection. Since volume of injection has been shown to be an important factor impacting the tolerability of SC injections (Heise 2014), the smaller injection volume associated with the 100 mg injection may offer some advantage in this population.

The 300 mg Q4W regimen was chosen to be included as a dosing option with less frequent injections. With this regimen, in children  $\geq 6$  to  $< 12$  years old and weight  $> 30$  kg, simulated dupilumab exposure at steady-state, specifically  $C_{max}$ ,  $C_{trough}$ , and weekly area under the curve (AUC) were lower than for the 200 mg Q2W. Study R668-AD-1021 demonstrated that efficacy for the 300 mg Q4W regimen was statistically superior to placebo in adults. Pharmacokinetic simulations have shown that in children with weight  $> 30$  kg, the steady-state exposure was higher for the 300 mg Q4W regimen than in adults with the same regimen, but is not expected to exceed that for adults receiving 300 mg Q2W.

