1.2.3. Modifications from the Statistical Section in the Final Protocol

None.

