5. STATISTICAL METHODS

For continuous variables, descriptive statistics will include the following: the number of patients reflected in the calculation (n), mean, median, standard deviation, first quartile (Q1), third quartile (Q3), minimum, and maximum.

For categorical or ordinal data, frequencies and percentages will be displayed for each category.

All data will be summarized by 3 treatment groups (i.e. dupilumab q2w dose, dupilumab q4w dose and placebo).

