5.8. Analysis of Safety Data

The summary of safety and tolerability will be performed based on SAF.

The safety analysis will be based on the reported AEs, clinical laboratory evaluations, physical examination, vital signs and 12-lead ECG.

Thresholds for treatment-emergent Potentially Clinically Significant Values (PCSVs) in laboratory variables and vital signs are defined in [Appendix 10.4](#). Treatment-emergent PCSV is any PCSV developed or worsened in severity compared to the baseline during the treatment and follow-up period.

The time interval to detect any event or abnormality is between the first injection of study medication and EOS.

Subgroups are defined by key baseline factors recorded on the CRF and listed to be considered for safety analyses:

- Age group (≥ 6 to < 9 , ≥ 9 to < 12)
- Sex (Male, Female)
- Ethnicity: Hispanic or Latino (no/yes)
- Race (White, Black, Asian, Other)
- Duration of AD (< 5 years, ≥ 5 years)
- Baseline BMI (< 20 , ≥ 20)
- Baseline weight group (< 30 kg, ≥ 30 kg)

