5.8.1. Adverse Events

Listings of TEAEs, serious TEAEs, and TEAEs resulting in death and study drug discontinuation will be generated.

Number and proportions of patients reporting TEAEs will be summarized for overall during the study, during the week 16 treatment period and during the follow-up period separately, sorted by decreasing frequency of SOC and PT based on the overall incidence for the combined dupilumab treatment groups.

Summaries of TEAEs will include:

- TEAEs
 - TEAEs by SOC/PT
 - TEAEs by SOC/HLT/PT
 - TEAEs by PT
 - Common TEAEs by SOC/HLT/PT (incidence with PT $\geq 5\%$)
 - Common TEAEs by SOC/HLT/PT (incidence with PT $\geq 2\%$)
 - TEAEs by severity by SOC/PT

- Severe TEAEs by SOC/PT
- TEAEs related to study medication as assessed by the investigator by SOC/PT
- Severe TEAEs related to study medication as assessed by the investigator by SOC/PT
- Serious TEAEs by SOC/PT
 - Serious TEAEs by SOC/PT
 - Serious TEAEs by SOC/HLT/PT
 - Serious TEAEs related to study medication as assessed by the investigator by SOC/PT
- TEAEs leading to permanent discontinuation of study treatment by SOC/PT
- Death by SOC/PT
- AESI by AESI category (see [Appendix 10.4](#)) and SOC/PT

The time to first AESIs (TEAE category), serious TEAE, or TEAE leading to permanent treatment discontinuation during the treatment period will be assessed by Kaplan-Meier estimates (K-M plot). In order to detect any safety signals, the hazard ratio (HR) will be provided together with the corresponding 95% confidence interval (CI) for the selected adverse events during the treatment period only. Hazard ratios will be calculated using a Cox model including treatment group and randomization strata as factors. The time is defined as the date of first specific event – the date of first dose + 1. Patients without a specific event will be censored at the end of treatment period.

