10.5. Search Criteria for TEAE of Special Interest/TEAE Syndrome¹

AESI	Search Criteria
Anaphylactic reactions	
For SMQ “anaphylactic reaction” An algorithmic approach will be used. A case must include either:
 
 1. A narrow term (a term from Category A); 2. Patient with both a term from Category B AND a term from Category C; 3. Patient with a term from Category D AND { a term from Category B - OR a term from Category C } 
For bullets 2 and 3, the search terms that are included under the SMQ for a particular event need to have the same start date (for e.g. if search shows cough (category B term) occurring at day 3 and urticaria (category C term) occurring at day 7, this event is not adjudicated as anaphylactic reaction as this is inconsistent with the clinical presentation of anaphylaxis as an acute event with simultaneous involvement of 2 or more body systems.
 
Note: manual adjudication of relevant PTs will be required by the study medical monitor, before database lock

Systemic or severe hypersensitivity reactions	
Hypersensitivity: Narrow SMQ for hypersensitivity excluding preferred term equal to dermatitis atopic or eczema
 
For systemic hypersensitivity, events in which 2 or more body systems are involved (as defined by System Organ Class) would be considered for adjudication based on further medical judgement
 
For severe hypersensitivity, an additional search will be done;
 
 - HLT = Injection site reactions and Severity = “severe” - HLT = Allergies to foods, food additives, drugs and other chemicals and Severity = “severe” or Serious=“Yes” 
Note: manual adjudication of relevant PTs will be required by the study medical monitor, before database lock

Malignancy	
 • SMQ “Malignant tumours” • SMQ “Tumours of unspecified malignancy”
Helminthic infections ²	-HLT = Cestode infections

	
-HLT = Helminthic infections NEC
 
-HLT = Nematode infections
 
-HLT = Trematode infection

Suicidal behavior	
Include the following PTs
 
 • Completed suicide • Suicidal ideation • Suicide attempt • Depression suicidal • Suicidal behavior

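### The SAP does not carry forward the protocol's separate placebo Q2W and placebo Q4W safety summaries, so injection-related events are seen only against a pooled placebo that matches neither active schedule

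*Protocol*

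**What the plan says.** Protocol 10.5 sets the general rule: "All placebo patients will be pooled for analysis regardless of whether it is 100 mg placebo, 200 mg placebo, or 300 mg placebo". Protocol 10.5.3 then makes a specific addition for safety. After the summary for each treatment group, "safety data for the placebo Q2W group and placebo Q4W group will be summarized separately".

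SAP 5 states: "All data will be summarized by 3 treatment groups (i.e. dupilumab q2w dose, dupilumab q4w dose and placebo"). SAP 5.8 adds only that "The summary of safety and tolerability will be performed based on SAF". No split of placebo by schedule appears in SAP 5.5 (dose administration), 5.6 (exposure), 5.8 to 5.8.5 (safety) or the summary table in 10.1. The SAP names the two placebo schedules only where it describes the design (2.1 and 2.3). SAP 1.2.3, headed "Modifications from the Statistical Section in the Final Protocol", contains the single word None.

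**The concern.** Placebo patients are split 1:1 between the two schedules within each weight stratum, so the pooled placebo column mixes two injection experiences. Each active arm has only one of them. For events caused by the act of injecting, a contrast with pooled placebo mixes any drug effect with a schedule effect.

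The protocol treats such events as important. Section 3.2.4.2 lists injection site reactions as very common (10% or more) in the adult programme, and section 3.2.2 says that "volume of injection has been shown to be an important factor impacting the tolerability of SC injections". The pooled contrast also goes beyond simple counts. The severe hypersensitivity search in SAP 10.5 includes "HLT = Injection site reactions and Severity" equal to severe, and for the time-to-event safety analyses in SAP 5.8.1 "Hazard ratios will be calculated using a Cox model including treatment group and randomization strata as factors", with a single placebo level.

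Collection also follows the schedule. The two-hour post-dose observation falls on day 1 and weeks 2 and 4 for Q2W, but on day 1 and weeks 4 and 8 for Q4W. Injection pain at week 2 is recorded only in Q2W patients.

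At stake is the tolerability picture for each of the two regimens. The primary efficacy result is not affected.

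**Working it through.** The plan gives no figure for this point, so there is nothing to reproduce. The check compares the texts (set out above), counts injections and volumes, and illustrates what pooling does under two assumptions.

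**Inputs.** Loading dose of 2 injections on day 1 (Protocol 7.1). Q2W dosing from week 2 to week 14 and Q4W dosing from week 4 to week 12 (Protocol 5.1). Placebo volumes of 0.7 mL (Q2W, below 30 kg), 1.14 mL (Q2W, 30 kg or more) and 2 mL (Q4W), with placebo split 1:1 (Protocol 5.1, SAP 2.1).

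**Planned injections.**
- Q2W: 2 + 7 (weeks 2, 4, 6, 8, 10, 12, 14) = 9
- Q4W: 2 + 3 (weeks 4, 8, 12) = 5
- Pooled placebo: (9 + 5)/2 = 7
- Ratio to pooled placebo: 9/7 = 1.29 for Q2W and 5/7 = 0.71 for Q4W

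**Planned total volume.**
- Below 30 kg: Q2W 9 × 0.7 = 6.3 mL; Q4W 5 × 2 = 10 mL; pooled placebo 8.15 mL
- 30 kg or more: Q2W 9 × 1.14 = 10.26 mL; Q4W 10 mL; pooled placebo 10.13 mL

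**Assumption A: equal risk q per injection whatever the volume, no drug effect, injections independent.** The risk of at least one reaction is 1 − (1 − q)^9 for Q2W and 1 − (1 − q)^5 for Q4W. Pooled placebo is the mean of the two. The documents give no q, so a range is shown.

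| q | Q2W | Q4W | Pooled placebo | Difference from pooled (points) | Risk ratio Q2W / Q4W |
|---|---|---|---|---|---|
| 0.5% | 4.4% | 2.5% | 3.4% | +1.0 / −1.0 | 1.28 / 0.72 |
| 1% | 8.6% | 4.9% | 6.8% | +1.9 / −1.9 | 1.28 / 0.72 |
| 2% | 16.6% | 9.6% | 13.1% | +3.5 / −3.5 | 1.27 / 0.73 |
| 5% | 37.0% | 22.6% | 29.8% | +7.2 / −7.2 | 1.24 / 0.76 |

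**Assumption B: expected reactions proportional to total volume, no drug effect.** The ratio to pooled placebo is the ratio of volumes.
- Below 30 kg: Q2W 6.3/8.15 = 0.77; Q4W 10/8.15 = 1.23
- 30 kg or more: Q2W 10.26/10.13 = 1.01; Q4W 10/10.13 = 0.99

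Under B the sign reverses in the lighter stratum and the effect nearly disappears in the heavier one. Against the matching placebo, the schedule-driven difference is zero under either assumption, because the number of injections and the volume are the same on both sides within each weight stratum.

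**The case against.** The strongest reply is that the SAP has not contradicted the protocol. Its three-group sentence closely follows one in Protocol 10.5, where it coexists with the separate placebo summary in 10.5.3. The entry None in SAP 1.2.3 can be read as meaning that the protocol's commitment still stands. That is fair: the SAP is silent and does not expressly cancel the split, and a reader should not infer a deliberate change of analysis. But SAP 1 describes the document as a comprehensive and detailed account of the analysis. A programmer working from it would produce one placebo column, and nothing in it would prompt the second view.

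It can also be said that the pooled presentation is the protocol's own choice, that adverse event tables are mostly counts and percentages, that injection-site reactions are not an AESI category of their own, and that exposure already uses separate Q2W and Q4W formulas with injections listed per patient. All of this stands. It limits the loss to an additional view. Patient listings do not replace a summary.

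A reader might infer from the injection counts that the Q2W arm will look worse and the Q4W arm better than it is. The documents do not support that. The inference needs equal risk per injection, while Protocol 3.2.2 itself says that volume matters, and volume per injection runs the other way.

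A reader might also take the protocol to promise a formal comparison of each regimen with its matching placebo, or a split of the Faces pain score. It promises neither. It commits to separate safety summaries, and SAP 4.4.3 lists Faces pain among the other efficacy variables.

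**Conclusion.** The omission is real and undeclared: a safety summary promised in Protocol 10.5.3 has no counterpart in the SAP. Its consequence is confined to events that depend on the injection schedule, for which pooled placebo (mean 7 injections) matches neither Q2W (9) nor Q4W (5). The injection counts and volumes follow from the documents and rest on full planned dosing.

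The direction and size of any distortion cannot be determined from the documents. The null ratios of 1.24 to 1.28 and 0.72 to 0.76 rest on an assumed equal risk of 0.5% to 5% per injection and ignore volume and clustering within patients. The volume-proportional ratios (0.77 and 1.23 below 30 kg; 1.01 and 0.99 at 30 kg or more) rest on an equally untested assumption. That the sign depends on the assumption is itself a reason to show the matching placebo. The point should be corrected, but it does not threaten the efficacy conclusions.

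**What to change.** In SAP 5.8, add placebo Q2W and placebo Q4W columns to the safety tables, as Protocol 10.5.3 promises, and keep the pooled placebo column. Lay out injection-site reactions, and exposure in SAP 5.6, so that each dupilumab regimen stands beside its matching placebo. No test is needed. If the sponsor prefers not to split, SAP 1.2.3 should declare the change and give the reason.

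Showing the Faces pain score in the same way would be a useful option, but it goes beyond what the protocol commits to.

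The cost is two descriptive columns drawn from data already collected, with no effect on alpha or on study conduct. The drawback is precision: with about 110 placebo patients split 1:1, each column holds about 55.

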### 10.5.3.1. Adverse Events

#### Definitions

For safety variables, 2 observation periods are defined:

- The pretreatment period is defined as the time from signing the ICF to before the first dose of study drug.
- The treatment-emergent period is defined as the day from first dose of study drug to end of study. The treatment-emergent period includes the 16-week treatment period and follow-up period.
  - Treatment period: date of the first dose of study drug to week 16 visit date (study day 113 starting from the first dose of study drug if week 16 visit date is unavailable) or early termination date, whichever comes first.
  - Follow-up period: date after week 16 visit date (study day 113 starting from first dose of study drug if week 16 visit date is unavailable) to end of study.

Treatment-emergent adverse events are defined as those that are not present at baseline or represent the exacerbation of a preexisting condition during the on-treatment period.

